*Ho1: CRT+IDC will be more effective than Game-Play Placebo+IDC in reducing heavy drinking days and decreasing days of use as measured by Breathalyzer and Timeline Follow-back Method (TLFB) during the 90 days of active intervention.*

**Secondary Aim #1:** To determine if CRT+IDC is more effective than Game-Play Placebo+ IDC in sustaining decreased alcohol use in older Veterans at the end of 6 months (3 months after the active intervention period).

*Ho2: CRT+IDC will be more effective than Game-Play Placebo+IDC in reducing heavy drinking days and decreasing days of use as measured by Breathalyzer and Timeline Follow-back Method (TLFB) for the 30 days preceding 6 month follow-up.*

**Secondary Aim #2:** To determine if the combination of CRT and IDC is more effective than game play placebo and IDC in improving neurocognitive functioning.

*Ho3: Veterans receiving CRT+IDC will show greater improvement than Veterans receiving Game-Play Placebo+IDC at 3 month follow-up on a global index of neurocognitive function, and on an index of working memory and an index of executive function.*

*Ho4: Differential improvements in neurocognitive function will be sustained at 6 month follow-up*

**4. Background:** Alcohol Use Disorders (AUDs) have a significant public health impact, cost billions of dollars in the US each year for treatment and lost productivity, and are highly prevalent in Veterans. Estimated point prevalence is 5.5% in returning Veterans, higher than the 3.8% civilian estimate. Lifetime prevalence for Vietnam Era Veterans was much higher when examined approximately 15 years after the end of the war, at almost 40% in men as compared to male civilians at 30%. Psychosocial behavioral interventions have some efficacy, but as revealed in a large VA cooperative multi-site study of a pharmacological augmentation (naltrexone), a high proportion in all arms of the study relapsed within one year. A recently published study of the relative efficacy of mindfulness-based relapse prevention in a civilian sample reported that 19% in the treatment as usual condition had returned to heavy drinking within 3 months. AUD is a major cause of suffering and functional disability for Veterans and a common co-morbidity with other physical and mental disorders. There is, therefore, a critical need to explore ways to improve treatment for AUDs in Veterans.

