**Procedures:**

Informed Consent and HIPAA authorization will be obtained according to procedures approved by the VACHS IRB. A certificate of confidentiality will be requested.

Randomization: Participants will be randomized into CRT+IDC or Game-Play Placebo+IDC conditions. Randomization will be stratified by neurocognitive deterioration (Yes/No) based on having 3 or more baseline cognitive measures greater than 1 SD below premorbid estimate (3 was the median number of measures below expected value in the pilot R21 study described above). Variable block randomization tables will be created based on computer generated blocks using random permuted blocks of 2 to 6 by our statistician from Yale Center for Analytic Science. Sealed envelopes containing the randomization by participant entry number will be created and opened when a participant's pre-randomization procedures are completed.

Assessments Procedures: Measures are listed in the table above. Preliminary screening will be performed with a brief interview usually by phone that describes the inclusion and exclusion criteria in simple language and asks if the individual believes he/she meets criteria. After informed consent, participants will undergo DSM-V diagnostic procedure with the M.I.N.I diagnostic interview adapted to DSM-V., the WTAR to determine reading level and pre-morbid IQ estimate and a thorough demographic and psychosocial interview to determine whether they are eligible for the study according to inclusion and exclusion criteria. Information from medical records and referring clinicians are also used. During the active intervention participants will have weekly Breathalyzer tests and a weekly TLFB Alcohol Use Calendar. Critical events will also be recorded along with on-going process data about participation in procedures and response to cognitive training. Treatment utilization will be tracked weekly and at follow-ups by chart review and interview. Baseline assessments will be repeated at 3 months and 6 months. A briefer battery of cognitive tests will be performed at 7 weeks. The participant time line is shown in the table below:

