## **Data Management, Sample Size Calculation, and Analysis Plan**

Data management will follow procedures established in previous studies. Our research team will use Teleforms® software to create, clean, and enter quantitative data. Forms are created with barcodes that are scanned using Teleforms' object character recognition software. Data is extracted and automatically inputted to an SPSS database. Filters flag data that needs to be re-checked by a person such as unclear characters, out-of-range variables and logical inconsistencies. The research assistant will scan files monthly so that errors can be readily corrected and consequential differences between treatment types (e.g., different levels of attrition) can be monitored closely. SPSS (vers. 21) will be used as the primary analysis software. Baseline characteristics will be tested for any significant differences between randomized conditions using parametric and non-parametric procedures as required by the nature of the data. Data reduction is a major issue in a relatively small N, large-number-of-variables study. We have chosen a primary outcome measure (Heavy Drinking Days and Days of Use in the first 90 days) to reduce Type I error. Heavy Drinking Days and Days of Use will be determined by Time-Line Follow-back calendar and Breathalyzer results. If a participant cannot provide more exact information about days of use for that week, then we will assume continuous use.

Neuropsychological data will be indexed into established domain scores (attention, working memory, memory and learning, executive function, processing speed) and a composite index score. The design is intent-to-treat. Distributions of continuous data will be tested for normality and transformed when necessary. Randomized conditions will be tested for potential differences on baseline values. We believe that our stratified randomization will make it unlikely that significant differences will be found; however, any significant differences will be used as covariates in between-group comparisons.

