Analysis Plan: We will use a Poisson regression model accounting for over-dispersion to compare the CRT+IDC arm to the Game-Play Placebo+IDC arm on the primary outcomes: Days of Use and Days of Heavy Drinking at 90 days (Ho1). We will use the same model to compare the CRT+IDC arm to the Game-Play Placebo+IDC for the 6 month time point, a secondary endpoint (Ho2). We will conduct sensitivity analysis using a negative binomial model and assess any differences in the results compared to the Poisson model with over-dispersion. To evaluate neurocognitive functioning (global index; index of working memory; index of executive function, etc..), we will use generalized estimating equations and/or linear mixed models (if the data appear normally distributed) to account for the correlation between time points (baseline, 3 months, 6 months) for a given individual. We will test for a significant treatment arm by time interaction to determine whether the combination of CRT+IDC is more effective than Game-Play Placebo+IDC in improving neurocognitive outcomes (Ho3, Ho4). We use contrast statements to explore the individual time point effects. In all models, we will adjust for neurocognitive functioning (the stratification variable). We will use the Benjamini-Hochberg procedure to control the false discovery rate for all secondary outcomes keeping the overall level of significance at 0.05. However, given the limited sample size in this study, we do not expect to reach statistical significance unless there are large effects, especially for the secondary outcomes, and thus plan to use these results as hypothesis generating for a larger confirmatory study.

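### The neurocognitive model names neither a common baseline mean nor a baseline-score covariate, so on the usual reading Ho3 and Ho4 rest on a change-score contrast that is less precise than it could be

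*Combined protocol and SAP*

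**What the plan says.** Ho3 (Purpose, Secondary Aim 2) predicts that the CRT+IDC arm "will show greater improvement than Veterans receiving Game-Play Placebo+IDC at 3 month follow-up on a global index of neurocognitive function", and on working-memory and executive-function indices. Ho4 predicts that the difference persists at 6 months.

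The Analysis Plan paragraph of the Combined protocol and SAP (Data Management, Sample Size Calculation, and Analysis Plan) proposes GEE and/or linear mixed models to "account for the correlation between time points (baseline, 3 months, 6 months) for a given individual". Baseline is therefore one of three repeated responses. The test is stated as: "We will test for a significant treatment arm by time interaction to determine whether the combination of CRT+IDC is more effective". Single visits are handled separately: "We use contrast statements to explore the individual time point effects".

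Every model adjusts for the stratification variable. The Randomization paragraph under Procedures defines it as a Yes/No factor "based on having 3 or more baseline cognitive measures greater than 1 SD below premorbid estimate". No other covariate is named for these models.

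The data-management paragraphs of the same section add that arms will be compared at baseline and that "any significant differences will be used as covariates in between-group comparisons".

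The plan does not say whether the arms share one baseline mean or have one each.

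**The concern.** Randomisation makes the expected baseline means equal. A model that estimates a separate baseline mean for each arm subtracts chance baseline noise in full from the follow-up difference. A model that uses the known equality, or regresses follow-up on baseline, removes only the predictive part of that noise and so gives a smaller standard error from the same data.

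What is at stake is precision. In the pilot described under Background, the arms differed on cognitive indices but not on substance-use outcomes, so Ho3 and Ho4 have the best prior support in this trial. The Analysis Plan itself says that the sample is limited and that the secondary results are meant to inform a larger study. Tighter estimates would serve that purpose.

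**Working it through.** **Inputs from the documents.** 1:1 allocation; at least 40 per arm analysed at 3 months (Sample size); a further 5–10% loss by 6 months (Sample size); pilot effects d = 0.84 (working memory), 0.72 (executive function), 0.36 (global index) and 0.71 (global index, AUD participants only), all under Background.

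**Assumptions.** The documents give no SD, no baseline-to-follow-up correlation ρ and no power for the indices, so there is no planned figure to reproduce. I take ρ from 0.5 to 0.8, equal SDs at both visits, effects in units of that SD, and a two-sided 5% test.

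**Step 1: what the planned contrast is.** With arm, time and arm-by-time in the model, each arm has a free mean at each visit. With complete data the 3-month interaction contrast is

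(mean at 3 months − mean at baseline) in CRT+IDC, minus the same in Game-Play Placebo+IDC,

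which is the difference in mean change, whatever the covariance.

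**Step 2: does the stratum term help?** A stratum main effect adds the same amount at each visit, so it cancels from a within-person change. Any other time-constant covariate main effect cancels in the same way.

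**Step 3: variances, in units of σ².**
- Change score: 2(1 − ρ) per participant, so SE = √(4(1 − ρ)/n) with n per arm.
- Common baseline or baseline-adjusted: 1 − ρ² per participant, so SE = √(2(1 − ρ²)/n).
- Ratio: (1 − ρ²)/(2(1 − ρ)) = (1 + ρ)/2. Saving: (1 − ρ)/2.

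| ρ | Change | Common baseline | Saving | 40 per arm acts like |
|---|---|---|---|---|
| 0.5 | 1.00 | 0.75 | 25% | 53 |
| 0.6 | 0.80 | 0.64 | 20% | 50 |
| 0.7 | 0.60 | 0.51 | 15% | 47 |
| 0.8 | 0.40 | 0.36 | 10% | 44 |
| 0.9 | 0.20 | 0.19 | 5% | 42 |

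The last column is 40 divided by (1 + ρ)/2.

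**Step 4: power of a single contrast, Φ(d/SE − 1.96), 40 per arm.** At ρ = 0.6 the SEs are √(4 × 0.4/40) = 0.200 and √(2 × 0.64/40) = 0.179.

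| d | Change score | Common baseline |
|---|---|---|
| 0.36 | 44% | 52% |
| 0.50 (illustrative) | 70% | 80% |
| 0.71 | 94% | 98% |
| 0.72 | 95% | 98% |
| 0.84 | 98.7% | 99.7% |

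At ρ = 0.5 the figures are 36% to 46% for d = 0.36 and 90% to 96% for d = 0.72. At ρ = 0.8 they are 72% to 77% for d = 0.36.

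**Step 5: simulation with stratification and dropout.** 1,500 trials per setting, 45 per arm, three visits, known covariance, stratified randomisation with an assumed correlation of 0.6 between the variable underlying the stratum and baseline. Dropout was set at 10% at 3 months and a further 8% at 6 months.
- Complete data: the unconstrained contrast matched the change-score difference to four decimals with the stratum main effect included. The common-baseline saving was 20%, 14% and 10% at ρ = 0.5, 0.65 and 0.8.
- With dropout: the two estimates were no longer identical but correlated 0.989 to 0.996. The saving was 18%, 12% and 8%.
- Using stratum-by-time in place of the stratum main effect left the variance of the unconstrained contrast essentially unchanged (0.0425 and 0.0425 at ρ = 0.5, complete data).

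**Step 6: the imbalance-triggered rule.** Taking significance at 5%, each baseline variable triggers adjustment about 5% of the time under randomisation. The pilot's baseline differences in the notes to Figures 1 and 2 (3.445, SE 2.627, p = .196; 3.067, SE 2.263, p = .183) would not have triggered it. If it did trigger, a covariate entered only as a main effect would cancel as in Step 2.

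**The case against.** The strongest objections are these.

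- **The plan does not state separate baseline means.** Correct: the parameterisation is not given. A reader might infer that the plan commits to them, but the text does not go that far. What remains is that an arm-by-time test ordinarily carries an arm main effect, and that the pilot, analysed with the same three-visit design and interaction test, reported estimated between-arm baseline differences. Nothing in the Analysis Plan departs from that.
- **The plan already has a route to baseline adjustment.** It does, but only after a significant imbalance, so it seldom applies (Step 6).
- **The size rests on unstated quantities.** True. Besides ρ, the formula needs equal SDs. At ρ = 0.6 with follow-up SD k times baseline, the ratio is k²(1 − ρ²)/(1 + k² − 2ρk): 0.8464/0.9425 = 0.90 at k = 1.15 and 0.4624/0.7025 = 0.66 at k = 0.85, against 0.80 at k = 1.
- **At the pilot's larger effects the planned test is already well powered.** Also true: the gain is about 1 to 3 points at ρ = 0.6 and 3 to 7 at ρ = 0.5 for d = 0.72 to 0.84. Pilot effects may be optimistic, and the Benjamini-Hochberg step lowers power under either model.
- **The figures describe one contrast.** The overall interaction over three visits has 2 degrees of freedom, so the power values do not carry over to it.

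A reader might also take 10–25% as the share of the achievable variance reduction that is given up. It is not. Relative to ignoring baseline, the achievable reduction is ρ² and the amount forgone is 2(1 − ρ) − (1 − ρ²) = (1 − ρ)². The share is therefore ((1 − ρ)/ρ)²: 100%, 44%, 18% and 6% at ρ = 0.5, 0.6, 0.7 and 0.8. The 10–25% is the reduction in variance of the effect estimate.

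**Conclusion.** The point holds as a minor efficiency issue. The baseline handling is not specified, and on the ordinary reading the 3-month contrast is a change-score comparison: exactly so with complete data, nearly so with the expected dropout. A common-baseline or baseline-adjusted model would lower its variance by about 25% to 10% for ρ of 0.5 to 0.8, or roughly 18% to 8% in the simulation with stratification and dropout. These sizes depend on the assumed ρ and equal SDs. The power gain matters for small to moderate effects and is slight at the pilot's working-memory and executive-function effects.

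A reader might infer that the planned analysis is biased or inflates type I error. The documents do not support that: the change-score contrast is valid under randomisation. The outcomes concerned are secondary and described as hypothesis generating.

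**What to change.** In the Analysis Plan paragraph, specify for each index a linear mixed model with:
- categorical time;
- one baseline mean common to both arms, with arm entering only at follow-up visits (or, alternatively, follow-up scores as the only responses with baseline score-by-time as covariate);
- stratum-by-time terms;
- unstructured covariance.

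Read Ho3 from the 3-month arm difference and Ho4 from the 6-month arm difference.

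In the data-management paragraphs, state that this baseline adjustment applies unconditionally to these models and does not depend on a baseline significance test.

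The cost is a few lines of wording. No new data are needed and the planned software can fit the model.

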deteriorated. These findings add justification to focusing our cognitive training on processes that support learning, memory and executive function, cognitive functions required to benefit from recovery-oriented treatment and to remain abstinent.

There were also differences noted in the R21 between those with a primary diagnosis of AUD (n = 28) and other SUDs (n = 20) with greater frequency of learning, memory and executive function decline and impairment in alcohol dependent participants and greater frequency of impairment in attention and response inhibition for participants with other SUDs. These group differences on performance measures were also mirrored in a self-report measure, the Barratt Impulsivity Scale, with other SUD participants scoring more than one standard deviation higher scores (more impaired) than AUD participants on Attention and Non-

planning subscales. These findings indicate that these two groups differ in type of cognitive impairment and is a primary reason that we have decided to focus on Veterans with AUD for the proposed submission.

We got excellent participation. Those randomized to the CRT+WT condition had an average of 213 hours of productive activity, performed an average of 39.6 (median = 42.8) hours of cognitive training and attended on average 10.4 (median = 12) out of 13 weekly groups. The WT Only group had similar total hours of productivity and group attendance. Follow-up rates were also very good, with 44 out of 48 (95.7%) completing 3 months follow-up and 42 out of 48 (87.5%) completing 6 month follow-up. Thus, this pilot demonstrated excellent adherence and study retention, well above what is usually found in SUD research.

[figure not shown]
Neurocognitive outcomes were analyzed by creating 5 composite indices: Visual and Verbal Working Memory, Visual and Verbal Learning, Processing Speed, Attention, and Executive Function. Mixed effects model for 3 points in time (Baseline, 3 month and 6 month follow-up) revealed significant Time effects on all indices and significant differences (TimeXCondition) favoring CRT+WT on the Visual and Verbal Working Memory Index ( $p < .01$ ; ES Cohen's  $d = .84$ ) and on the Executive Function Index ( $p < .05$ ; ES Cohen's  $d = .72$ ). All index trends favored the CRT+WT condition, and a Global Index Composite Score showed a non-significant trend with an Effect Size of Cohen's  $d = .36$ .

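### Does testing Ho3 (3 months) and Ho4 (sustained at 6 months) with one arm-by-time interaction leave the cognitive hypotheses undecided?

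*Combined protocol and SAP*

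**What the plan says.** The Project Description (Secondary Aim #2) states two cognitive hypotheses. Under Ho3, Veterans on CRT+IDC "will show greater improvement than Veterans receiving Game-Play Placebo+IDC at 3 month follow-up", on a global, a working memory and an executive function index. Ho4 reads: "Differential improvements in neurocognitive function will be sustained at 6 month follow-up".

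The Analysis Plan fits one repeated-measures model (GEE and/or linear mixed) per index, "to account for the correlation between time points (baseline, 3 months, 6 months) for a given individual". It labels a single test with both hypotheses: "We will test for a significant treatment arm by time interaction to determine whether the combination of CRT+IDC is more effective". The next sentence adds: "We use contrast statements to explore the individual time point effects". The Benjamini-Hochberg procedure is then applied "to control the false discovery rate for all secondary outcomes keeping the overall level of significance at 0.05". The section closes by saying that large effects would be needed for significance, especially on secondary outcomes, and that the authors "plan to use these results as hypothesis generating for a larger confirmatory study".

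The Measures section lists neurocognition at 7 weeks, 3 months and 6 months as secondary outcomes. The model in the Analysis Plan does not include 7 weeks.

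**The concern.** An arm-by-time interaction over three visits is an omnibus test. A significant result says that the arms changed differently somewhere. It does not say at which visit, and as a two-sided test it does not by itself say in whose favour. Yet it carries the labels of two hypotheses that differ only in the visit.

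The contrasts that could separate them are described as exploratory, and neither is named as the test of Ho3 or Ho4. No criterion is given for *sustained*. The coding of time is not stated, and the pilot figures in the Background report slopes, which leaves linear time possible. A named secondary outcome, cognition at 7 weeks, has no model or contrast.

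At stake is whether a report could claim a 3-month benefit from an effect that appeared only at 6 months, or choose the deciding result after seeing the data.

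**Working it through.** **Plan's own figures.** The documents give no power figure for the cognitive outcomes. The only ones are for drinking: detectable reductions of 37% and 55%. They reproduce with the Poisson regression formula (N = 80, two-sided 0.05): 37.0% for days of use, and 54.2% for heavy drinking days (81% power at the stated 55%). This point does not rest on them.

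**Inputs.** From the sample-size paragraph: 40 per arm. Assumed, because the documents are silent: effect 0.5 SD, equal correlation ρ = 0.5, 0.7 or 0.8 between visits, categorical time, complete data, two-sided 0.05. Results are given in the order ρ = 0.5/0.7/0.8.

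**Interaction.** Let d = (d₃, d₆) be the arm differences in change from baseline, in SD units. Their covariance is V = (2/n)(1−ρ)[[2,1],[1,2]], and the 2-df test has non-centrality d′V⁻¹d.

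- For d = (0.5, 0): (n/2)/(1−ρ) × (2/3) × 0.25. At ρ = 0.7 this is (20/0.3) × 0.1667 = 11.11, so power is 86%.
- For d = (0, 0.5), (0.5, 0.5) and (−0.5, 0) the value is again 11.11.
- Over the three correlations, power is 63/86/96% in every case.

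So the interaction cannot assign the effect to a visit. Exact equality comes from equal correlation. Under AR(1) it rejects in 72/94/99% for 3 months only and 53/75/90% for 6 months only or both, and still does not identify the visit.

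**Contrasts already in the plan.** Each has SE = √(4(1−ρ)/n). At ρ = 0.7 this is √(4 × 0.3/40) = 0.173, so z = 0.5/0.173 = 2.89 and power is Φ(2.89 − 1.96) = 82%.

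| True effect (0.5 SD) | Interaction | 3-month contrast | 6-month contrast |
|---|---|---|---|
| 3 months only | 63/86/96% | 61/82/94% | 5% |
| 6 months only | 63/86/96% | 5% | 61/82/94% |
| Both | 63/86/96% | 61/82/94% | 61/82/94% |

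The contrasts separate the hypotheses. If *sustained* is read as both contrasts significantly favouring CRT+IDC, it is reached in 45/72/90% of trials with an effect at both visits.

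**Time coding.** With equally spaced visits, linear time and equal correlation, the slope weights are (−1, 0, 1). The interaction then sees only the 6-month change: 5% for a 3-month-only effect, 61/82/94% otherwise. But under linear time the 3- and 6-month contrasts would be fixed multiples of one slope and share one p-value. A plan to look at individual time point effects makes sense only if time is categorical.

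**Week 7.** With complete data and equal correlation, adding week 7 to the model changes the precision of the two contrasts by 0%. With 10% lost by week 13 and a further 7.5% by week 26, the gain is 0.5–4.6% for the 3-month contrast and 0.2–2.3% for the 6-month contrast. Entered as a fourth level it would make the interaction a 3-df test, which a week-7-only effect of 0.5 SD would trigger in 62/86/97% of trials.

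**A stricter rule.** Suppose the interaction must be significant before a contrast counts. Power for Ho3 with a 3-month-only effect falls from 61/82/94% to 54/79/93%. If the interaction must pass the strictest step of a three-index family (0.05/3 = 0.0167), it is 42/70/89%. The secondary family is larger: five domains, a composite, two 6-month drinking outcomes and craving make at least nine. At 0.05/9 = 0.0056 it is 30/58/83%.

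**The case for a change.** The strongest case for a change is this. The plan states formal hypotheses and applies false discovery rate control, and both need defined tests. Read literally, the interaction decides Ho3. With a 6-month-only effect, 93/94/95% of significant interactions come with a non-significant 3-month contrast, so a literal reader would credit Ho3 when nothing happened at 3 months. Week 7 is named as a secondary outcome without qualification. Writing the missing lines would cost nothing in visits or tests.

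Much of this is correct as a description of the text. The contrasts are not designated, *sustained* is not defined, the p-values that enter the Benjamini-Hochberg set are not listed, and 7 weeks has no stated analysis.

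It does not show harm. The 93–95% figure is the planned 3-month contrast behaving as it should; it misleads only a team that ignores a contrast it planned. That a two-sided test also rejects when placebo does better is true of any two-sided test, and the estimate shows the direction. Ho3 and Ho4 already fix the visit, the comparison and the direction, and Ho3 also names the three indices, so little is left to choose after seeing the data.

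The one substantive alternative, gating the contrasts behind the interaction, is a trade-off: it orders the tests within an index but costs power. Whether the contrasts belong inside or outside the false discovery rate family is also open to argument.

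The shorter 7-week battery described under Assessments Procedures does not conflict with the schedule. That visit omits the Addiction Severity Index, the Beck scales, VR-12, WHODAS and PAOFI, so it is briefer than the 3- and 6-month visits even with every cognitive test given.

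**Conclusion.** No change follows. The interaction alone cannot distinguish Ho3 from Ho4: 63/86/96% rejection in all three patterns, given 40 per arm, an assumed 0.5 SD effect, equal correlation of 0.5/0.7/0.8 and categorical time. But the same model and the next sentence of the plan supply the two contrasts that can. There are exactly two follow-up visits in the model and one hypothesis for each, so an analyst would match them without difficulty and would read *sustained* as a benefit at 6 months as well as at 3.

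Week 7 is a reporting gap of little consequence: it bears on neither hypothesis, would add at most about 5% precision, and can be summarised descriptively. All of this concerns secondary outcomes that the plan presents as hypothesis generating. The primary drinking analysis is untouched. A stricter decision rule would cost power with no clear gain.
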